### **13.3 Consent Process**

Before volunteering to participate in this study, subjects are explained by an investigator about the study objective, method, advantages, and disadvantages, including side effects that may be caused by tofacitinib. Subjects have the right to choose to participate or not participate in a voluntary research study without coercion or persuasion and have the right to terminate their participation in the study at any time. The termination will not affect the current and future medical care that the subjects will receive. When subjects decide to participate in the study, they will be asked to sign their first and last name in the informed consent before enrolling.

### **13.4 Data Collection**

In this study, subjects' personal records were separated into a specific form with limited access to the data. The data was recorded using a programmed computer, and the confidentiality of the data was protected. A password is required to access the data of the subjects. Persons who can access the subjects' data are the research physician, research team, research sponsor, and the Institutional Review Board Committee.

### **13.5 Data Analysis**

The research data was then comparatively assessed using the SPSS program.

### **13.6 Statistics used in data analysis**

13.6.1 General data will be calculated by using Univariate analysis as a percentage, standard deviation, range, mean

13.6.2 Treatment efficacy will be evaluated by bivariate analysis calculated for a percentage of hair loss area at 12 and 24 weeks, compared with pre-treatment data using One-way ANOVA.

13.6.3 Side effects from treatment will be presented with event frequency, the number and the percentage of subjects in each event will be compared using Friedman Two-way Analysis.

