## **7. The objective of this study**

### **7.1 Primary objective**

To study the effectiveness and safety of tofacitinib in Thai patients with recalcitrant and extensive AA at 24 weeks

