8.1.2 Gender: Male and Female

8.1.3 Age: Subjects aged 18 years or older

8.1.4 Number of subjects: calculated from the formula

$$n = \frac{Z_{\alpha/2}^2 P(1-P)}{d^2}$$

$$Z_{\alpha/2} = 1.96$$

$$P = \text{Proportion of the population who had improvement} = 0.87$$

$$d = \text{A maximum tolerated error determined by an investigator} = 0.2$$

$$n = \frac{(1.96)^2(0.8)(1-0.8)}{(0.2)^2} = 16$$

Therefore, the number of subjects should be approximately 16. Given approximately 20% of the number of patients who may have missed follow-up treatments, a total of 19 subjects are planned to be collected.

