12.2. To be presented at academic conferences both in Thailand and abroad

## 13. Methods of conducting research and place for conducting study/data storage

### 13.1 Study design

This is a prospective cohort study conducted at the Institute of Dermatology. Nineteen male and female Thai volunteers with extensive hair loss of more than 50% of the head area were recruited.

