### 13.2 Conducting research procedures

13.2.1 The principal investigator selects the volunteers according to the inclusion and exclusion criteria.

13.2.2 The principal investigator takes a personal history of the volunteers, such as date of birth, age, ethnicity, age of onset, stage of disease progression, past medical history, weight, and height.

13.2.3 The principal investigator will ask the volunteers about their health, pre-existing disease conditions such as allergies, asthma, thyroid disease, psoriasis, vitiligo, autoimmune diseases, rheumatoid arthritis, diabetes, irritable bowel syndrome, immunodeficiency states, current medications, or medications taken or treated prior to the administration for 1 month, severe illness and severe stress.

13.2.4 The principal investigator examines the condition of the scalp, hair, and body by measuring the area of hair loss on the scalp, including the body hair by recording the SALT score, hair loss on the body, and examining the nail characteristics.

$$\frac{\text{SALT BL} - \text{SALT F/U}}{\text{SALT BL}} \times 100\% = \% \text{ change from baseline.}$$

13.2.5 All subjects will have photos taken from the side, back, and top of their scalp with a stereotactic device.

13.2.6 All subjects will undergo tests prior to treatment, including complete blood count, lipid profiles, anti-HIV, HBs Ag, Anti HCV, renal function test (BUN, Cr), liver function test (LFT), urine pregnancy test (UPT; female), chest x-ray, stool exam.

13.2.7 All subjects will be asked to take Tofacitinib 5 mg twice a day.

13.2.8 All subjects will be evaluated after the treatment every four weeks during the 24-week duration of the treatments. The SALT score is assessed each time, including the potential side effects. Also, they will have photos taken from the side, back, and top of their scalp with a stereotactic device every visit. The treatment with tofacitinib is successful should subjects have hair regrowth more than 50% compared to the baseline photo.

13.2.9 All subjects are required to have blood tests later for CBC, cholesterol, triglyceride, low-density lipoprotein (LDL), LFT, BUN, and Cr after weeks 4, 12, 24 of treatments.

13.2.10 All female subjects are required to have UPT every four weeks during the 24-week duration of the treatments.

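### Section 13.6.2 names a one-way ANOVA for repeated hair-loss measurements on the same subjects without stating a within-subject form; run as written, its error term is wrong

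*Combined protocol and SAP*

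**What the plan says.** Section 13.6.2 gives the efficacy analysis in one sentence: the "percentage of hair loss area at 12 and 24 weeks, compared with pre-treatment data using One-way ANOVA". It mentions no pairing, subject factor, repeated-measures form, follow-up contrast or interval. It is the only efficacy test named in the text available for this review.

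The design makes the data repeated measures:

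- Section 13.1: "This is a prospective cohort study conducted at the Institute of Dermatology". Section 13.2.7 gives every subject the same treatment, so time is the only factor an ANOVA could have.
- Section 13.2.4 records hair loss by SALT and defines a percentage change from each subject's own baseline.
- Section 13.2.8: "All subjects will be evaluated after the treatment every four weeks during the 24-week duration of the treatments". SALT is scored at each of these visits.

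The primary objective (7.1) concerns "effectiveness and safety of tofacitinib in Thai patients with recalcitrant and extensive AA at 24 weeks". For side effects, 13.6.3 names a within-subject rank test: "the percentage of subjects in each event will be compared using Friedman Two-way Analysis".

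**The concern.** An independent-groups one-way ANOVA assumes that the baseline, week-12 and week-24 values come from different people. Here they come from the same people and will be correlated. The ANOVA error would then include stable differences between subjects, which cancel when each subject is compared with his or her own baseline. It would also apply one pooled variance to visits whose spread may differ a good deal once some subjects regrow hair and others do not.

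At stake is whether the named efficacy test has its stated error rate and uses the information in a cohort of 16 to 19 subjects. With positive correlation and similar SDs, the test is too conservative and loses power. With very unequal SDs, the error can go the other way for a single comparison with baseline.

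**Working it through.** **1. The plan's own figure.** Section 8.1.4 uses n = 1.96² × P(1 − P) / d². With the values in its worked line, 3.8416 × 0.8 × 0.2 / 0.04 = 15.37, rounded up to 16; 16 × 1.2 = 19.2, stated as 19. (The section defines P as 0.87 but calculates with 0.8; that is a separate matter.) This is a precision formula for a proportion, with no SD, correlation or ANOVA in it, so the sample size does not depend on 13.6.2. I take n = 16 as the number analysed.

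**2. Assumed inputs.** The documents give no SD, correlation or week-12 effect. Assumed: SD 25 SALT points at each visit; common correlation ρ of 0.3, 0.5 or 0.7; mean fall of 10 points by week 12 and 20 by week 24; two-sided 5% level.

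**3. Why the overall F goes wrong.** With equal SDs and common ρ, the expected time mean square is n Σ(μₜ − μ̄)² / 2 + σ²(1 − ρ). The first term is 16 × (100 + 0 + 100) / 2 = 1600. The one-way error has expectation σ² = 625; the repeated-measures error has expectation 625(1 − ρ).

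| ρ | Time MS | One-way error | Ratio | Repeated-measures error | Ratio |
|---|---|---|---|---|---|
| 0.3 | 2037.5 | 625 | 3.26 | 437.5 | 4.66 |
| 0.5 | 1912.5 | 625 | 3.06 | 312.5 | 6.12 |
| 0.7 | 1787.5 | 625 | 2.86 | 187.5 | 9.53 |

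Stronger correlation should help. Under the one-way form it hurts slightly. With no change, the one-way ratio centres near 1 − ρ instead of 1, so the test rejects too rarely.

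**4. Simulated size and power** (trivariate normal, 40,000 trials per setting, n = 16):

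| ρ | One-way F power | Greenhouse-Geisser F power | One-way F rejection under no change |
|---|---|---|---|
| 0.3 | 46% | 61% | 1.7% |
| 0.5 | 43% | 76% | 0.4% |
| 0.7 | 40% | 94% | under 0.1% |

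At n = 19 the powers are 55/53/52% against 70/85/98%. With SD 25 and a 40-point fall at n = 16, both F tests have at least 97%.

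**5. Which week is affected.** For one comparison with baseline, the ratio of pooled to true standard error is √[2v̄ / (v₀ + vₜ − 2cov₀ₜ)], where v̄ is the mean of the three variances.

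- Equal SDs, common ρ: the ratio is 1/√(1 − ρ) = 1.20/1.41/1.83, the same at both weeks.
- SDs 15/30/20, ρ = 0.5: 2v̄ = 2 × (225 + 900 + 400)/3 = 1016.7. Week 12: 225 + 900 − 450 = 675, ratio 1.23. Week 24: 225 + 400 − 300 = 325, ratio 1.77. Week 24 is worse.
- SDs 5/15/40, ρ = 0.3: 2v̄ = 2 × (25 + 225 + 1600)/3 = 1233.3. Week 12: 25 + 225 − 45 = 205, ratio 2.45. Week 24: 25 + 1600 − 120 = 1505, ratio 0.91. The week-24 error is now too small: under no change, an unadjusted pooled week-24 contrast rejects 8.3% and the overall one-way F 5.9%.

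The plan names no such contrasts. They only show that the direction is not fixed; the overall-F results in step 4 are the ones that describe the plan as written.

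**The case against.** The strongest reply is that the wording is only loose. A one-way ANOVA can have time as its single within-subject factor; 13.2.4 defines a per-subject change; 13.6.3 names Friedman, so the authors had repeated measures in mind at least there. This stands as a possibility. It does not settle the matter: section 13.5 names only SPSS, without a procedure, and 13.6.2 read literally leads an analyst to the independent-groups test.

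A second reply is that the consequence is limited. This also stands in part. The primary time point is week 24, the cited effects are large, and success is defined per subject: "The treatment with tofacitinib is successful should subjects have hair regrowth more than 50% compared to the baseline photo". That is the kind of proportion the sample size was built on. But 13.6.2 is still the efficacy test the plan names, and week 12 is one of its two comparisons.

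Two stronger readings are tempting, and the documents support neither. A reader might infer that the damage falls mainly at week 12. That pattern needs SDs that widen or correlations that fade over time, and the documents give neither; with equal SDs and a common correlation the standard error is equally wrong at both weeks, and with SDs 15/30/20 week 24 is worse. A reader might also infer that the plan would produce false claims of efficacy. The week-24 inflation shown above needs an eightfold spread of SDs; with similar SDs and positive correlation the error is lost power.

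**Conclusion.** The point holds. As written, 13.6.2 applies a test for independent groups to correlated measurements on the same subjects, and its error term does not match the design. That follows from the design, not from any assumed figure.

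The size does rest on assumptions. For a moderate effect (20 points, SD 25, n = 16, ρ 0.3 to 0.7), the overall test gives up about 15 to 54 percentage points of power (61 − 46 to 94 − 40), and its true size is well below 5%. For a large effect (40 points, SD 25), both forms detect it almost always, so a large week-24 benefit would probably still be seen. Whether week 12 or week 24 is affected more, and whether the week-24 error is too large or too small, cannot be known from the documents. The sample size is not affected. It should be fixed, because the remedy is nearly free and the planned cohort is small.

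**What to change.** In 13.6.2, replace the one-way ANOVA with one within-subject analysis, chosen before the data are seen. Suggested text: *The change in SALT score from baseline will be tested by paired t-tests at week 12 and at week 24, each reported as mean change with a 95% confidence interval, with Holm adjustment for the two comparisons.* Each paired test uses the variance of its own change, so it does not rely on equal variances across visits.

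A one-way repeated-measures ANOVA with Greenhouse-Geisser correction is an acceptable alternative. If that is what was meant, stating it and the correction is enough. Leave the regrowth criterion in 13.2.8 as it is.

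Cost: one sentence. No new data, visits or subjects are needed, since SALT is already recorded at baseline and every four weeks, and SPSS can run paired tests.

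### 13.6.2 compares weeks 12 and 24 with baseline but names no deciding contrast, so the planned efficacy test is not tied to the week-24 question in 7.1

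*Combined protocol and SAP*

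**What the plan says.** Section 7.1 fixes the time point of the main question: "To study the effectiveness and safety of tofacitinib in Thai patients with recalcitrant and extensive AA at 24 weeks". Section 13.2.8 schedules assessments more often than that ("All subjects will be evaluated after the treatment every four weeks during the 24-week duration of the treatments") and defines success without a time point: "The treatment with tofacitinib is successful should subjects have hair regrowth more than 50% compared to the baseline photo".

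Section 13.6.2 is the only efficacy analysis in the available text. It evaluates "percentage of hair loss area at 12 and 24 weeks, compared with pre-treatment data using One-way ANOVA". It does not rank the two weeks. It names no contrast, follow-up test, testing order, significance level or multiplicity rule, and labels neither week as exploratory. Section 13.6 also plans no analysis of the success proportion. One part of the document directly after 13.6.3 was not available, so these statements cover the visible text only.

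**The concern.** The objective asks one question, about week 24, and the test that should answer it contains two follow-up times of equal standing. There are two ways to read 13.6.2.

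- **One ANOVA over baseline, week 12 and week 24.** The null hypothesis is that all three means are equal. Rejecting it says that some mean differs, not that week 24 differs from baseline. Regrowth present at week 12 and lost by week 24 could still give a significant efficacy p-value.
- **Two comparisons with baseline.** Either could be reported as the efficacy result, and the plan does not say which one counts.

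This is separate from the fact that one-way ANOVA ignores that the same subjects are measured three times. Changing to repeated-measures ANOVA or to paired tests leaves both readings open.

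Sections 11 and 17 expect the results to inform treatment and policy decisions. A reader of a single-arm study of 19 people needs to know which comparison answers the stated question.

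**Working it through.** **1. The plan's own figure, and what its 1.96 is for.** Section 8.1.4 uses n = z²P(1−P)/d² with z = 1.96 and d = 0.2.

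- With the substituted P = 0.8: 3.8416 × 0.16 / 0.04 = 15.37, so 16. This reproduces the plan ("Therefore, the number of subjects should be approximately 16").
- With the defined P = 0.87: 3.8416 × 0.1131 / 0.04 = 10.86, so 11. This does not reproduce it, and is a separate inconsistency.
- 16 × 1.2 = 19.2, given as 19.

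The 1.96 sets the precision of one proportion. No significance level is stated for 13.6.2, so the 5% used below is an assumption.

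**2. Inputs for the checks.** From the documents: 19 subjects, 20% loss (19 × 0.8 = 15.2, about 15 completers), and three time points. Assumed: normal data, SD 20 points, within-subject correlation 0.3–0.7 (0.5 as the central value), two-sided 5%.

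**3. Reading as one overall F test, true effect at week 12 only.** n = 15, correlation 0.5; the table shows the share of trials significant.

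| Mean hair-loss area at baseline / week 12 / week 24 | One-way F | Repeated-measures F | Paired week 24 vs baseline |
|---|---|---|---|
| 85 / 65 / 85 | 83% | 97% | 5% |
| 85 / 70 / 85 | 48% | 82% | 5% |

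A second set of runs used n = 16 and 19, correlations 0.3–0.7 and week-12-only gains of 0.5 to 1.0 SD:

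- One-way F significant in 11–89% of trials (n = 16) and 16–96% (n = 19).
- Repeated-measures F significant in 37–99.9% (n = 16) and 43–100% (n = 19).
- The paired week-24 test stayed at about 5% throughout.
- At n = 16, correlation 0.5 and a 0.8 SD gain, the overall test was significant while the paired week-24 test was not in 56% of trials (one-way) or 84% (repeated measures).

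**4. Reading as two comparisons with baseline, no true effect.** The family-wise rate is 1 − P(|Z₁| ≤ 1.96 and |Z₂| ≤ 1.96). With equal within-subject correlation ρ, the two changes share a baseline and their correlation is (1 − ρ) / [2(1 − ρ)] = 0.5.

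- Valid tests: 9.1% at correlation 0.5 between the tests (9.75% at 0, 7.0% at 0.9). Simulated paired tests at n = 15 to 19 give about 9%.
- Independent-groups comparisons, as one-way ANOVA implies: about 4%, 1.5% and 0.2–0.3% at within-subject correlations 0.3, 0.5 and 0.7. They reach about 9% only at correlation 0.

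The independent-groups test is conservative here. It takes the variance of a mean change as 2σ²/n, when the true value is 2σ²(1 − ρ)/n.

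**5. With one deciding contrast.** A paired week-24 comparison at 5% has a false-positive rate of about 5% (simulated 4.8–5.2%) whatever happens at week 12. The planned sample size is unaffected, because it does not come from this test.

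**The case against.** The strongest reply is that the intended time point is already clear. Section 7.1 names 24 weeks, and week 24 is one of the two times in 13.6.2. The wording there, including its description of the analysis as bivariate, points to comparisons with pre-treatment values rather than to a bare overall F test. The study is a single-arm cohort sized for precision, where formal error control matters less than in a confirmatory trial. All of this is fair and limits the point. What it does not supply is a link from 7.1 to a test, since 13.6.2 ranks neither comparison.

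Two stronger inferences are tempting, and the documents do not support them.

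- **That the plan as written nearly doubles the false-positive rate.** It does not. The named test treats visits as independent groups and is conservative at any plausible positive correlation (step 4). The 9% figure arises only after the pairing is corrected. Nor can 1.96 in 8.1.4 be taken as the alpha of this test.
- **That 83% or 97% is the expected risk.** Those figures come from a constructed case with a full 1 SD gain at week 12 and none at week 24. Treatment is planned through week 24, and section 9 cites clinical improvement in about 54–81.9% over six months. Nothing in the documents predicts that regrowth would vanish. The figures show what the overall test does and does not test.

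**Conclusion.** The point holds in a limited form. The objective is set at week 24, and the only visible efficacy test neither isolates week 24 nor says which comparison decides.

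Under the overall-test reading, a significant result need not concern week 24 at all. Under the two-comparison reading, the choice of which result to report is left open. That choice carries an inflated error rate (about 9% against an assumed 5%) only once valid paired tests are in use, so the ranking and the pairing correction should be made together.

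The SD, correlation, effect sizes and 5% level are assumptions. The practical consequence is confined to transient or borderline results; with large, sustained regrowth every version of the analysis would lead to the same conclusion. The change is worth making because it is nearly free and lets the analysis answer the objective.

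**What to change.** Reword 13.6.2 along these lines:

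*The deciding analysis of hair-loss area is the within-subject change from baseline to week 24, tested two-sided at 5% and reported with its 95% confidence interval. The change from baseline to week 12 is secondary: it is tested at 5% only if the week-24 test is significant, and is otherwise descriptive. An overall test across the three time points is not used to support the efficacy claim.*

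Presenting week 12 as purely descriptive would serve equally well. The fixed order holds the family-wise rate at 5% and takes no alpha from week 24. The within-subject wording corrects the pairing at the same time.

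This ranks the time points for hair-loss area only. It should not displace the proportion with more than 50% regrowth in 13.2.8, which is the kind of quantity that 8.1.4 sizes the study for.

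The cost is a short rewording, with no extra subjects, visits or data. The small downside is that week 12 cannot be claimed as confirmatory if week 24 is not significant.

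### The safety summary in 13.6.3 covers only events attributed to treatment, in a cohort without a control group, with no all-cause summary and no confidence interval

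*Combined protocol and SAP*

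**What the plan says.** - **Objective (7.1).** Effectiveness and safety at 24 weeks together form the primary objective.
- **Design (13.1, 13.2.7).** "This is a prospective cohort study conducted at the Institute of Dermatology". All subjects are to take tofacitinib; no comparison group is described.
- **Collection of clinical events (13.2.8).** At the four-weekly visits, "The SALT score is assessed each time, including the potential side effects". There is no definition of an adverse event, no statement that events are noted regardless of cause, and no rule for judging cause.
- **Laboratory safety (13.2.9).** Blood count, lipids, liver and renal tests are done on all subjects after weeks 4, 12 and 24.
- **After treatment (13.2.11).** A follow-up is required four weeks after stopping. The section does not say what is recorded there.
- **Analysis (13.6.3).** "Side effects from treatment will be presented with event frequency". The same item adds the number and percentage of subjects per event and a Friedman comparison. It plans no interval and names no denominator.
- **Size (8.1.4).** The calculation rests on the proportion improved and gives 16, raised to 19 for losses.

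**The concern.** Read literally, 13.6.3 reports events caused by the drug. An event that the investigator thinks unrelated then falls outside the summary, and the plan has no second summary to catch it. Section 9 names four common effects. Two of them, headache and upper respiratory tract infection, also occur in people who take no drug. Without a comparison group, nobody can tell in the individual subject which of these events the drug caused. Whoever decides what counts therefore sets the reported rate, and the plan gives no rule for that decision. If an event is not recorded at the visit because it seemed unrelated, no later analysis can restore it.

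The second part is precision. A percentage from 19 subjects carries wide uncertainty, and the plan shows none of it. Sections 11 and 17 say that the results are meant to inform patients, doctors and policymakers. For those readers, a zero count without an upper limit is easy to take as more reassuring than it is.

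**Working it through.** **Inputs**
- Planned number: "a total of 19 subjects are planned to be collected" (8.1.4).
- Number before the allowance: "the number of subjects should be approximately 16" (8.1.4).
- Allowance: "Given approximately 20% of the number of patients who may have missed follow-up treatments" (8.1.4).
- Z = 1.96 and d = 0.2 (8.1.4). P is printed as 0.87 in the definition and as 0.8 in the worked line.

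**Step 1. The plan's own figure.** n = Z² P(1 − P)/d² = 1.96² × 0.8 × 0.2 / 0.2² = 15.37, rounded up to 16. Then 16 × 1.2 = 19.2, about 19. Both figures reproduce with P = 0.8. With P = 0.87 the formula gives 10.86, so 11. The 7 may be a reference mark run into the number when the text was extracted, and nothing below depends on it. No event rate enters this calculation.

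**Step 2. What a zero count leaves open.** With no events in n subjects, the exact (Clopper-Pearson) two-sided 95% upper limit is 1 − 0.025^(1/n).
- n = 19: 1 − 0.025^(1/19) = 0.176, or 17.6%.
- n = 16: 1 − 0.025^(1/16) = 0.206, or 20.6%.

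Other conventions at n = 19:
- one-sided exact 95%: 1 − 0.05^(1/19) = 14.6%;
- rule of three: 3/19 = 15.8%;
- Wilson: 16.8%.

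All lie between about 15% and 18%, so the message does not depend on the method.

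**Step 3. How far attribution can move a rate.** If k of 19 subjects have a clinical event of a given kind, a summary limited to attributed events can show anything from 0 to k/19. The documents give no background rate, so k is an assumption:

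| k of 19 | All-cause rate | Possible reported rate |
|---|---|---|
| 2 | 10.5% | 0% to 10.5% |
| 6 | 31.6% | 0% to 31.6% |
| 10 | 52.6% | 0% to 52.6% |

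This shows only that the plan sets no limit on the spread. It does not estimate how many events would be left out.

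**Step 4. What belongs to sample size alone.** An event with a true rate of 5% is not seen at all with probability 0.95^19 = 0.377 in 19 subjects and 0.95^16 = 0.440 in 16. Wording and intervals do not change these probabilities; an interval only makes the limitation visible.

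**Step 5. Whether the planned test fills the gap.** The Friedman test compares repeated measurements within subjects. It yields neither an event rate with its uncertainty nor an upper limit.

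**The case against.** The strongest reply is that the protocol uses the term side effects loosely. Section 9 lists raised lipids and liver enzymes under it without any step of attribution, and 13.2.8 speaks of potential effects, which points away from a judgement made before recording. On that reading 13.6.3 may simply mean adverse events on treatment. A reader might infer from the wording that only events judged drug-related are written down. The documents do not support that: they describe no judging step, no person who judges and no rule for discarding events. What stands is that the scope of collection is undefined and that the scope of reporting is causally worded.

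Second, laboratory safety is measured in everyone under 13.2.9, and this covers two of the four common effects in Section 9. That is right, and it confines the attribution problem to clinical events. The missing interval affects both kinds.

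Third, a reader might infer that bare percentages are all that is planned. They are not: 13.6.3 also gives event frequency and number of subjects, and anyone with the count and the denominator can work out an interval. That is true, but 13.6.3 names no denominator, and few readers outside statistics would make the calculation.

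Fourth, the direction of error is not fixed. Leaving out events thought unrelated lowers the rate relative to the all-cause rate, and only if events are in fact left out. Relative to the drug-caused rate, open-label attribution can err either way. This stands, so no downward bias should be claimed as established.

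**Conclusion.** The point holds in this form: for a component of the primary objective, the plan's only safety summary is limited by its wording to treatment-caused events, in a cohort where cause cannot be verified, and it carries no measure of uncertainty. This is more than a missing detail, because following 13.6.3 as written gives a rate that depends on an unspecified judgement, and a better summary is available from the same visits.

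The firm number is the limit for a zero count: 17.6% at 19 subjects (two-sided exact 95%), or 20.6% if only 16 are counted. The size of any attribution effect cannot be given, because the documents hold no background event rates and the values of k above are illustrations. The conclusion assumes that 13.6.3 means what it says. If the investigators already intend to record and report all events, only the wording and the interval need to change.

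The change should be made, but the plan can be run without it.

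**What to change.** - **13.2.8:** state that all adverse events are recorded from first dose through the four-week post-treatment visit already required by 13.2.11, regardless of suspected cause, with the investigator's judgement of relatedness noted separately.
- **13.6.3:** report, for each event, the number and percentage of all dosed subjects with an exact (Clopper-Pearson) 95% confidence interval. Put all-cause events in the first column and events judged related in the second.
- **Safety conclusion:** state the largest rate not excluded. For an event not seen in 19 dosed subjects, this is 17.6%.

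The cost is rewording, a slightly longer event list and a safety figure that may look less favourable. No visits, tests or subjects are added. The change does not replace a control group, so all-cause rates still cannot be divided into drug effect and background, and it does not raise the chance of seeing a rare event.

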The safety and effectiveness of tofacitinib for AA treatment have been demonstrated in adults. In the three studies, subjects with extensive AA had clinical improvement of about 54-81.9% during the six months, and the Severity of Alopecia Tool (SALT) score was improved by 50-90% approximately.

The side effects of the treatment were mild. Subjects may develop headaches, hyperlipidemia, upper respiratory tract infection, and a slight increase in hepatic enzyme activity. Those side effects usually return to normal even after the patient did not stop taking the drug, and in very few cases, erythema, leg swelling, paleness, bone ischemia have been reported. However, no cancer was found in patients taking the drug yet, though, the company has a warning about this in the drug leaflet.

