13.2.11 When AA subjects finish treatments either at week 24, or resolved before, or discontinue tofacitinib due to the side effects before the end of the treatments, they are required to have a follow-up after four weeks of discontinuation.

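### Section 13.6.3 compares side-effect frequencies with a Friedman test without saying what is compared; in this single-arm study the p-value does not measure how many subjects are harmed

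*Combined protocol and SAP*

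**What the plan says.** Safety stands beside effectiveness in the primary objective (section 7.1). The whole plan for analysing it is one sentence, section 13.6.3: side effects are "presented with event frequency, the number and the percentage of subjects in each event will be compared using Friedman Two-way Analysis". It names no conditions, null hypothesis or significance level. Section 13.6.2, on efficacy, does name its time points.

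The design has no comparator. Section 13.1 states: "This is a prospective cohort study conducted at the Institute of Dermatology". Section 13.2.7 states: "All subjects will be asked to take Tofacitinib 5 mg twice a day". Visits are every four weeks to week 24, and section 13.2.8 adds: "The SALT score is assessed each time, including the potential side effects". No pre-treatment side-effect assessment is described. Laboratory tests are done before treatment (13.2.6), and 13.2.9 repeats "CBC, cholesterol, triglyceride, low-density lipoprotein (LDL), LFT, BUN, and Cr after weeks 4, 12, 24 of treatments".

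Section 13.2.11 expects some subjects to finish early, because the disease "resolved before, or discontinue tofacitinib due to the side effects before the end of the treatments", and asks for a follow-up four weeks after stopping.

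**The concern.** A Friedman test ranks several conditions within each subject and asks whether they differ. For event counts in a single arm, the conditions can be only event types or visits. Neither comparison is the safety question in the primary objective, which is how many treated subjects have each side effect and how precisely that is known.

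What is at stake is interpretation. A non-significant result could be reported as reassurance when it reflects only that events were spread evenly over visits or over event types. Under the across-visit reading there is a second problem. The test needs a value at every visit, so subjects who stop because of side effects leave the comparison unless their missing visits are filled in. The available text does not say how missing visits are handled.

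**Working it through.** **Inputs.** n = 19 from section 8.1.4 (16 × 1.2 = 19.2, taken as 19). Six on-treatment visits at weeks 4, 8, 12, 16, 20 and 24 (13.2.8). For event types, the four common ones in section 9: "Subjects may develop headaches, hyperlipidemia, upper respiratory tract infection, and a slight increase in hepatic enzyme activity". The plan gives no side-effect rates and no figure for this comparison, so there is nothing to reproduce and **every event pattern below is an assumption**. The patterns show what the test can do, not what is likely.

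**Formula.** On yes/no data, the tie-corrected Friedman statistic equals Cochran's Q:

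Q = (k − 1)(k ΣCⱼ² − T²) / (kT − ΣRᵢ²), on k − 1 degrees of freedom,

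where k is the number of conditions, Cⱼ the events in condition j, Rᵢ the events in subject i, and T the total.

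**Visits as conditions (k = 6), each affected subject having one event**

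| Affected | Timing | Q | p |
|---|---|---|---|
| 18/19 | three per visit | 5(6×54 − 18²)/(108 − 18) = 0/90 = 0 | 1 |
| 6/19 | one per visit | 5(6×6 − 6²)/(36 − 6) = 0/30 = 0 | 1 |
| 6/19 | all at week 4 | 5(6×36 − 6²)/(36 − 6) = 900/30 = 30 | 0.000015 |
| 3/19 | all at week 4 | 5(6×9 − 3²)/(18 − 3) = 225/15 = 15 | 0.010 |

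These are chi-square p-values. Exact within-subject permutation gives 6 × (1/6)⁶ = 0.0001 for the third row and 6 × (1/6)³ = 0.028 for the fourth. Rows two and three have the same number affected and differ only in timing. Rows one and four reverse the order of harm.

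If the same six subjects are affected at all six visits, numerator and denominator are both 0 and there is no p-value.

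**Adding other time points**

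- *Event-free baseline (k = 7).* 18/19 once each, three per visit: Q = 6(7×54 − 18²)/(126 − 18) = 324/108 = 3, p = 0.81. 3/19 affected at all six visits: Q = 6(7×54 − 18²)/(126 − 108) = 324/18 = 18, p = 0.006 (exact 1/49 = 0.020).
- *Event-free baseline and event-free follow-up visit (k = 8).* The same two patterns give Q = 756/126 = 6, p = 0.54, and Q = 756/36 = 21, p = 0.004.

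**Event types as conditions (k = 4)**

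- Four subjects per type, all different (16/19 affected): Q = 0, p = 1.
- Four subjects, all with one type (4/19 affected): Q = 3(4×16 − 4²)/(16 − 4) = 144/12 = 12, p = 0.007 (exact 4 × (1/4)⁴ = 0.016).
- Totals 8, 4, 2, 2 nested within 8 subjects: Q = 288/20 = 14.4, p = 0.0024. The same totals in 16 different subjects: Q = 288/48 = 6, p = 0.11.

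**Early stopping.** The sample-size section allows for loss: "Given approximately 20% of the number of patients who may have missed follow-up treatments". The allowance is 19 − 16 = 3 subjects. If three subjects are affected at week 4 and stop, and no one else is affected, the 16 complete rows contain no events. Q is then 0/0, while the incidence is 3/19.

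**What incidence gives instead.** The exact (Clopper-Pearson) 95% intervals depend only on the number affected. For 0/19 the upper bound is 1 − 0.025^(1/19) = 17.6%. For 3/19 the interval is 3% to 40%, for 6/19 13% to 57%, and for 18/19 74% to 99.9%.

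**The case against.** **The p-value does respond to the number harmed.** This is true when timing and overlap are fixed. With all events at week 4 and six visits, Q is 5 × the number affected. With persistent events against an event-free baseline, it is 6 × that number. A reader might infer that the p-value has nothing to do with how many are harmed. That goes too far: the number affected does not determine the p-value, but it does influence it.

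**A small p-value can carry information.** It can. With an event-free baseline, 3/19 persistently affected gives p = 0.006, which is evidence of a change on treatment. The stronger reading, that the test can say nothing about safety in either direction, is not supported. What fails is inferring safety from a large p-value, or the size of a risk from a small one.

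**Change over time is a fair question.** Section 9 says side effects usually return to normal on continued treatment, and a test across visits would address that. It is a secondary question, and 13.6.3 does not say that it is the one meant. A Friedman test of laboratory values at named times would also be legitimate, but 13.6.3 speaks of numbers and percentages of subjects with events.

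**The text may be incomplete.** A block directly after section 13.6 was removed before review. Statements that conditions, intervals or missing-visit rules are absent therefore apply only to the available text. The mismatch between the test and the safety question does not depend on that block.

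**The practical loss is small.** This stands: counts and percentages are planned anyway.

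**Conclusion.** The point holds in a limited form. As available, 13.6.3 does not say what the Friedman test compares. On either reading possible for event counts in this single arm, the test does not estimate how many subjects are harmed. The same 6/19 can give p = 1 or p = 0.000015, and 18/19 can give p = 1 where 3/19 gives p = 0.010. Adding a baseline or the off-treatment follow-up visit does not cure this: 18/19 spread evenly still gives 0.81 or 0.54.

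The loss of subjects who stop for side effects applies only to the across-visit reading, and only if missing visits are not filled in.

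Severity is minor to moderate. A reader might infer that the safety data themselves are compromised. They are not: the descriptive results remain valid, and no decision rule in the available text rests on the p-value. The conclusion about the test follows from its form; the particular p-values rest on assumed patterns.

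**What to change.** Drop the Friedman comparison as the safety analysis of event frequencies. For each side effect, report the number and percentage of all treated subjects with at least one event, keeping early stoppers in the denominator, with an exact (Clopper-Pearson) 95% confidence interval. Give the upper bound when no events are seen.

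If change over time is of interest, keep a Friedman test only as a secondary analysis with its time points named, for example laboratory values at baseline and weeks 4, 12 and 24. Report it with the within-subject change from baseline and a 95% confidence interval, and state how missing visits are handled.

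The cost is a change of wording and one small table, from data already planned to be collected. With 19 subjects the intervals will be visibly wide, which is a fair picture of what the study can say about safety.
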